Study Protocol

**Association Between Body Roundness Index and
Wound Healing Post-Thoracic Surgery: A Prospective
Study**

NCT ID not yet assigned

Unique Protocol ID: TJ-JRB202503009

Data:2025.05.01

Background

The thorax is a vital region of the human body, and the issue of postoperative wound healing following thoracic surgery has long been a subject of clinical concern. Thoracic surgeries—including cardiac surgery, thoracoscopic procedures, and open thoracotomy—are commonly performed for the treatment of cardiopulmonary diseases, tumors, and trauma. Although advancements in surgical techniques and medical equipment have significantly improved surgical success rates, complications such as wound infection, dehiscence, and poor cosmetic outcomes remain relatively common due to the high tension and extensive movement associated with the thoracic region[3]. Poor wound healing in the chest can have a profound impact on patients' psychological well-being, social interactions, and overall quality of life[4]. Excessive tension in soft tissues and skin is considered a key factor contributing to delayed healing and unfavorable scarring. Studies have identified gender, age, and the use of anticoagulants as risk factors for impaired wound healing, while serum lipids may play a protective role. Lipids are critically involved in modulating inflammation, angiogenesis, cellular proliferation, and tissue regeneration, all of which are essential processes in wound healing[5][9].

Obesity has emerged as a growing concern in modern medicine and now poses a serious threat to the health of a large proportion of the population. According to the *Chinese Guidelines for the Diagnosis and Treatment of Obesity*[7], both overweight and obesity exert profound negative effects on multiple organ systems, including the cardiovascular, respiratory, and gastrointestinal systems. Numerous studies have identified excessive obesity as a major risk factor for cardiovascular and cerebrovascular diseases, type 2 diabetes, and chronic kidney disease. In clinical practice, body mass index (BMI) is commonly used to assess obesity[17-19]. However, BMI has several limitations, as it cannot

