The research team conducted discussions and analyses to develop the study protocol, including inclusion and exclusion criteria and the clinical data required for statistical analysis. Clinical and follow-up data of enrolled subjects were collected through the HIS system of Tongji Medical College. Using SPSS version 26.0, subjects were grouped based on whether their wounds achieved secondary healing, and intergroup differences were analyzed to preliminarily identify potential factors associated with impaired wound healing. Subsequently, logistic regression analysis was performed to further determine risk factors influencing wound healing. Multivariate logistic regression analysis was then conducted to identify independent risk factors affecting wound healing. These findings aim to provide clinically feasible intervention strategies to promote more efficient and effective wound healing.

Participant Selection

Inclusion Criteria:

- Patients who underwent surgical treatment in the Department of Thoracic Surgery at Tongji Hospital;
- Complete clinical data and diagnostic test results available;
- Postoperative follow-up conducted regularly in accordance with medical advice, with comprehensive follow-up records;

Exclusion Criteria:

- Without surgery or transferred to other departments;

- Missing basic information;
- Failure to review on time or refusal to follow up;
- Additional surgeries within 30 days of discharge from the hospital;

Sample Size Calculation

A total of 400 patients undergoing thoracic surgery in the Department of Thoracic Surgery at Tongji Hospital, affiliated with Tongji Medical College of Huazhong University of Science and Technology, will be enrolled.

Study Procedure

The research team conducted a thorough literature review to gain a comprehensive understanding of the relevant background before initiating the study design. Inclusion and exclusion criteria, as well as the clinical data required for statistical analysis, were established accordingly. A total of 500 participants are planned for enrollment; subjects not meeting the exclusion criteria will be excluded.

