Upon admission, patient data including gender, age, height (m), weight (kg), waist circumference, abdominal circumference, hip circumference (cm), comorbidities (such as hypertension, coronary heart disease, diabetes), and preoperative laboratory values including cholesterol, triglycerides, and low-density lipoprotein (g/L) will be collected. Postoperatively, data on the surgical procedure and routine pathological findings will be recorded. Wound healing status will be assessed during a follow-up visit 30 days after surgery. Group comparisons based on wound healing status (healed versus secondary healing) at 30 days will be performed using independent t-tests. Potential factors influencing wound healing will be evaluated using logistic regression analysis. Variables demonstrating statistical significance in univariate analysis will be included in a multivariate logistic regression model. A p -value < 0.05 will be considered statistically significant. This analysis aims to identify independent

risk factors associated with poor chest wound healing and to propose feasible preventive measures accordingly.

References

- [5] Schlager JG, Hartmann D, Wallmichrath J, Ruiz San Jose V, Patzer K, French LE, Kendziora B.

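### Eligibility does not bar patients whose index operation treats an existing chest wound infection, dehiscence or non-healing wound, which can dilute or confound the BRI and lipid associations

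*Protocol*

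**What the plan says.** Under Participant Selection, the inclusion criteria ask for "Patients who underwent surgical treatment in the Department of Thoracic Surgery at Tongji Hospital", together with complete clinical data and regular follow-up. The indication for surgery is not limited.

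The exclusion criteria are four: "Without surgery or transferred to other departments"; "Missing basic information"; "Failure to review on time or refusal to follow up"; and "Additional surgeries within 30 days of discharge from the hospital".

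Data Collection and Statistical Analysis fixes the timing. Anthropometry is taken at entry ("Upon admission, patient data including gender, age, height (m), weight (kg), waist circumference, abdominal circumference, hip circumference (cm), comorbidities"), lipids are preoperative, and healing status (healed or secondary healing) is read 30 days after surgery. That section and Study Procedure also record the type of surgery and the procedure. Neither lists a field for wound or infection status before the operation.

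The Background says of thoracic surgery that "complications such as wound infection, dehiscence, and poor cosmetic outcomes remain relatively common". The stated aim is to find independent risk factors and to derive preventive measures from them.

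**The concern.** A prospective risk-factor study reads its associations forwards: the exposure is measured first and the outcome process follows. That order fails for a patient admitted to have a failed or infected chest wound treated. The wound problem is already under way when waist, weight and lipids are measured.

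Two consequences follow. First, such a patient has a high risk of non-healing at day 30 for reasons unrelated to BRI, so the BRI odds ratio is pulled towards 1. Second, if the illness has lowered weight, waist or lipids before measurement, low values become linked to non-healing through the existing wound state. The Background expects lipids to be protective, and lipids lowered by an existing wound problem would give the same pattern. If events are few, a handful of such patients can carry much of the information.

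**Working it through.** **Step 1: does any criterion close the gap?**

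| Criterion | Does it address a wound problem at admission? |
|---|---|
| Surgery in the department | No; any indication qualifies |
| Complete data; regular follow-up | No |
| No surgery, or transfer | No |
| Missing basic information | No |
| Missed or refused follow-up | No |
| Further surgery within 30 days of discharge | Only in part: it concerns later surgery, not the reason for the index operation |

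The last exclusion removes an enrolled patient who returns early for repair, and could be read to bar some early re-operations as new entries. Late wound failures, and patients first operated on elsewhere, remain eligible.

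**Step 2: share of cases.** The protocol gives no event rate and no share of such patients, so every rate here is an assumption. Let f be their share of entrants (1%, 3%, 5%), p = 70% their day-30 case probability, and r = 5% the risk in everyone else. With the 400 patients given under Sample Size Calculation:

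- f = 1%: 4 × 0.70 = 2.8 cases, against 396 × 0.05 = 19.8; share 2.8/22.6 = 12%
- f = 3%: 12 × 0.70 = 8.4, against 388 × 0.05 = 19.4; share 8.4/27.8 = 30%
- f = 5%: 20 × 0.70 = 14, against 380 × 0.05 = 19; share 14/33 = 42%

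Study Procedure gives 500 instead of 400. The shares and odds ratios do not depend on which figure is used.

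**Step 3: effect on a true BRI odds ratio of 1.5 per SD.** In ordinary entrants, logit(risk) = a + ln(1.5) × z, with z standard normal and a set so that the mean risk is r. In the others, risk is p regardless of z, and z is shifted by s. The univariate logistic slope in the mixture, found by numerical integration, gives:

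| r | s (SD) | f = 1% | f = 3% | f = 5% |
|---|---|---|---|---|
| 5% | 0 | 1.43 | 1.33 | 1.27 |
| 5% | −0.5 | 1.34 | 1.15 | 1.04 |
| 10% | 0 | 1.46 | 1.40 | 1.36 |
| 10% | −0.5 | 1.41 | 1.29 | 1.19 |

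Simulation agrees to within about 0.02. With p = 40%, r = 5% and s = −0.5, the values are 1.41, 1.27 and 1.17. No scenario crosses 1.

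**Step 4: a marker with no true effect, such as a lipid.** Assume p = 50%, r = 5% or 10%, and a marker 0.5 or 1.0 SD lower in these patients. False-positive rates are for a two-sided 5% test with 400 patients.

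| f | Spurious OR per SD | False-positive rate | Share of cases |
|---|---|---|---|
| 0 | 1.00 | 5.0% | 0 |
| 1% | 0.92 to 0.98 | 5.1% to 6.7% | 5% to 9% |
| 2% | 0.86 to 0.96 | 5.7% to 11.4% | 9% to 17% |
| 5% | 0.74 to 0.92 | 8.9% to 36.2% | 21% to 35% |

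With 500 patients, the last false-positive range is 9.9% to 43.5%.

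**Step 5: scale against sampling error.** With 400 patients the standard error of the log odds ratio is about 0.23 at 5% risk and 0.17 at 10%. A true 1.5 at 5% risk has a 95% interval of 1.5 × exp(±1.96 × 0.23), roughly 0.95 to 2.4. The bias at a 1% share lies well inside that.

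**The case against.** The strongest objection is that nothing shows these patients occur in useful numbers. The Background calls wound complications relatively common after thoracic surgery. It does not call them a common reason for operating in this department, and the indications it names are cardiopulmonary disease, tumours and trauma. Many wound complications may need no operation. This stands: the prevalence is unknown and could be negligible. It does not close the gap, because the Background is not an eligibility limit.

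A reader might infer more than the protocol supports, in three ways.

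- *The patients cannot be identified.* The protocol records type of surgery and procedure data, and a debridement or re-closure should often be visible there. What is lacking is a stated restriction or adjustment. A sensitivity analysis could also sit in an analysis plan not seen here.
- *The BRI association runs backwards.* With a true odds ratio of 1.5, the lowest value computed is 1.04. The mechanism for BRI is dilution and confounding by existing wound state. A spurious inverse association appears only for a marker with no true effect that the illness has lowered, which is more plausible for lipids than for BRI. That lowering is itself an assumption.
- *These patients already have the outcome.* The outcome is healing 30 days after the index operation. A failed wound that is excised and re-closed is a strong risk factor for that outcome, not the outcome itself.

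**Conclusion.** The gap is real on the text: an index operation for an existing chest wound infection, dehiscence or non-healing wound satisfies every criterion, and the exposures are then measured after that problem began. The consequence is possible dilution or confounding of the BRI association and a possible spurious lipid association; reversal of the BRI effect is not shown.

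The size cannot be determined from the protocol. Under the stated assumptions it is small when such patients are about 1% of entrants, where the false-positive rate for a null marker is at most 6.7%. It is material at about 3% to 5%, where a true BRI odds ratio of 1.5 falls to between 1.04 and 1.40 depending on incident risk and BRI shift. Because the share is unknown and the planned data could identify many of these patients, this is a point to consider rather than a required correction. The reason to act is the low cost, in a study that intends to name independent risk factors and preventive measures.

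**What to change.** Add one line to the Exclusion Criteria: *existing infection, dehiscence or non-healing of a chest wound at admission, or index operation performed to treat one*. Apply it from the admission diagnosis and the recorded type of surgery. If any such patients are already enrolled, repeat the BRI and lipid models without them and report both results.

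A wider field for active chest infection as the reason for surgery is not needed for this point; it would take in patients with no wound failure.

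The cost is one criterion and a check of data that are mostly collected already. The downside is a few patients fewer, and results that apply only to patients without a chest wound problem at entry.

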Data collection and follow-up will be conducted using the HIS system of Tongji Hospital. The variables to be collected include gender, age, height (m), weight (kg), waist circumference, abdominal circumference, hip circumference (cm), comorbidities (such as hypertension, coronary heart disease, diabetes), preoperative cholesterol, triglycerides, low-density lipoprotein (g/L), and type of surgery.

Data analysis will be performed using SPSS version 26.0. Initially, independent t-tests will be applied to compare groups based on wound healing status (healed vs. secondary healing) at 30 days postoperatively to identify potential factors associated with impaired wound healing. Variables identified as significant in univariate logistic regression analysis will be entered into a multivariate

logistic regression model. Statistical significance is set at $p < 0.05$. This analysis aims to determine independent risk factors for poor chest wound healing and to propose preventive measures accordingly, culminating in the completion of the study report.

Potential Risks and Mitigation Strategies

This study is observational in nature, with data collected exclusively by inpatient physicians at our hospital. Patient privacy will be strictly protected throughout the data collection process. If any issues related to poor wound healing arise during follow-up, the follow-up personnel will inform patients of appropriate subsequent treatment options. Patients lost to follow-up will be excluded from the study.

Data Collection and Statistical Analysis

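### Eligibility depends on attending follow-up after surgery, so final membership of this prospective cohort is settled only after the outcome window, and only compliant completers are analysed

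*Protocol*

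**What the plan says.** The title calls the work "A Prospective Study". Under Data Collection and Statistical Analysis, exposures are recorded at entry ("Upon admission, patient data including gender, age, height (m), weight (kg), waist circumference"), and wound status is assessed at a visit 30 days after surgery.

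Three rules then make membership depend on what the patient does after the operation:

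- Participant Selection, inclusion: "Postoperative follow-up conducted regularly in accordance with medical advice, with comprehensive follow-up records".
- Participant Selection, exclusion: "Failure to review on time or refusal to follow up".
- Potential Risks and Mitigation Strategies: "Patients lost to follow-up will be excluded from the study".

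A further exclusion, "Additional surgeries within 30 days of discharge from the hospital", also concerns an event after baseline. The protocol gives no visit window that would define a review as on time. Nowhere does it keep, count or describe the patients whom these rules remove.

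**The concern.** In a prospective cohort, entry should be decided by facts known when follow-up starts. A patient who then misses the outcome visit is a cohort member with a missing outcome. Here that patient is ineligible instead and disappears from the denominator.

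Attendance may plausibly be related to the wound. Patients who feel well may skip the visit, and patients who are unwell may be unable to come. It may also be related to comorbidity and adiposity. The rules therefore act on the study's outcome and on the association named in its title, from which the study intends to propose preventive measures. Because those removed are not counted, a reader could neither detect nor bound the distortion. The rule on late review may also discard a wound status that was actually observed.

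**Working it through.** **Timing check.** Each rule is set against the baseline (admission) and the outcome visit (day 30 after surgery).

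| Rule | Known at admission or surgery? | When it is settled |
|---|---|---|
| Regular follow-up with full records | No | During or after follow-up |
| Late or refused review | No | When the review falls due, or later |
| Lost to follow-up | No | After the visit is missed |
| Further surgery within 30 days of discharge | No | 30 days after discharge, which can be later than the day-30 visit |

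**No stated figure to reproduce.** The protocol gives no event rate, attrition rate or power calculation. It states 400 patients under Sample Size Calculation and 500 under Study Procedure. Reading these as analysed and enrolled would imply a loss of 1 − 400/500 = 20%, but both are described as enrolment, so this is not a planned attrition rate.

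**Illustration; all inputs are assumptions.** Take two equal BRI groups with risks of poor healing of 20% (high) and 10% (low).

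- True odds ratio = (0.20/0.80)/(0.10/0.90) = 2.25.
- True overall rate = 15%.
- Let r be the share retained in each cell. Observed OR = true OR × (r high-failed × r low-healed)/(r high-healed × r low-failed).
- Observed rate = retained failures / all retained.

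| Retention: high failed / high healed / low failed / low healed | OR factor | Observed OR | Observed rate | Lost |
|---|---|---|---|---|
| 80 / 80 / 80 / 80% | 1 | 2.25 | 15.0% | 20% |
| 95 / 75 / 95 / 75% (wound status only) | 1 | 2.25 | 18.3% | 22% |
| 64 / 80 / 72 / 90% (both, multiplicative) | (0.64×0.90)/(0.80×0.72) = 1 | 2.25 | 12.1% | 17.5% |
| 60 / 85 / 80 / 85% | (0.60×0.85)/(0.85×0.80) = 0.75 | 1.69 | 12.2% | 17.8% |
| 95 / 70 / 80 / 85% | (0.95×0.85)/(0.70×0.80) = 1.44 | 3.24 | 16.9% | 20.3% |

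Cells for the fourth row, as shares of each BRI group: high 0.20×0.60 = 0.12 failed and 0.80×0.85 = 0.68 healed; low 0.10×0.80 = 0.08 failed and 0.90×0.85 = 0.765 healed. OR = (0.12×0.765)/(0.68×0.08) = 1.69. Rate = 0.20/1.645 = 12.2%.

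The OR factor does not depend on the true risks. The last two retention patterns would turn a null odds ratio of 1.0 into 0.75 or 1.44.

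**The case against.** Several points on the other side stand.

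- **Bias in the odds ratio is conditional.** A reader might infer that the BRI odds ratio is biased whenever retention depends on both wound status and BRI. The third row of the table shows otherwise: if the two effects multiply, the odds ratio is untouched. Bias needs the failed-to-healed retention ratio to differ between BRI groups.
- **The rate is not the main target.** The Objective concerns associations, so a distorted rate of poor healing matters less than a distorted odds ratio.
- **Patients are not chosen by their outcome.** A reader might infer that the cohort is picked with outcomes in hand. The documents do not support that. Exposures are measured at admission, no criterion names wound status, and many non-attenders will have no day-30 status to know. What is settled late is final membership.
- **Late attenders.** A reader might infer that an open wound at a late review proves failure at day 30. It does not, because a wound can reopen; the Background itself lists dehiscence. With no window stated, it is also unclear who counts as late. The protocol supports only that such patients may be discarded.
- **Recovering outcomes from records can itself select.** Readmission and dressing entries mainly capture failures, so filling gaps selectively would push the rate upward. The fix has to guard against this.
- **Missing-data methods often belong in a statistical analysis plan**, which is not shown, and their absence is no fault here. But a plan cannot analyse as missing those patients whom eligibility has already removed, so the protocol wording is the proper target.

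**Conclusion.** The concern holds in a limited form. The protocol's own eligibility text conditions membership on conduct after baseline, restricts the analysis to patients who complied with follow-up, and leaves no count of the rest. That much rests on the wording alone.

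Whether the results are biased, by how much and in which direction cannot be known from the document. Unequal retention by wound status distorts the rate: under the assumptions above, a true 15% appears as anything from 12.1% to 18.3%. A non-multiplicative pattern distorts the odds ratio: a true 2.25 appears as 1.69 or 3.24. Equal, outcome-only and multiplicative retention leave it at 2.25. These figures use assumed risks, assumed retention of 60% to 95% and a two-group simplification of BRI. They show what is possible and do not predict what will happen.

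The change is still worth making, because it is cheap and outcomes not retained may be hard to recover later.

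**What to change.** 1. Delete the follow-up inclusion criterion and the whole exclusion for late or refused review. Define eligibility only by facts known at admission or surgery. Exclusions that can be judged then may stay.
2. Review the exclusion for further surgery after discharge on the same ground. It is post-baseline, and as worded it could remove re-operations for wound problems.
3. Replace the removal of patients lost to follow-up, under Potential Risks and Mitigation Strategies, with this rule: eligible operated patients stay in the cohort, and those without a day-30 assessment are counted as missing outcomes and reported by BRI and baseline characteristics.
4. State a visit window in advance, and use late visits within it whatever the wound status.
5. Apply any look-up in the hospital information system to all non-attenders by one rule. Use record-derived outcomes only in a sensitivity analysis, because records mainly capture failures.
6. Add one sensitivity analysis for missing outcomes (weighting or multiple imputation, with a bound). It may sit in the statistical analysis plan.

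Cost: a change of protocol wording, a records look-up and slightly more analysis, with no new visits or patients. The downside is that some missing outcomes are shown openly and some assessments do not fall exactly on day 30.

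### Eligibility depends on events after surgery, with no exception for wound-related reoperation, so wound failures can be removed from the cohort instead of counted

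*Protocol*

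**What the plan says.** The title calls the study prospective. Under Data Collection and Statistical Analysis, exposures are fixed early ("Upon admission, patient data including gender, age, height (m), weight (kg), waist circumference" and other items are collected) and the outcome has one time point: "Wound healing status will be assessed during a follow-up visit 30 days after surgery". Patients are then grouped as healed or secondary healing.

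Four rules make membership of the cohort depend on what happens after the operation:

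- Participant Selection, Exclusion Criteria: "Additional surgeries within 30 days of discharge from the hospital".
- Same list: "Failure to review on time or refusal to follow up".
- Participant Selection, Inclusion Criteria: "Postoperative follow-up conducted regularly in accordance with medical advice, with comprehensive follow-up records".
- Potential Risks and Mitigation Strategies: "Patients lost to follow-up will be excluded from the study".

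The reoperation rule is not limited by reason or site. The protocol nowhere says that an operation on the study wound counts as a healing failure. The exclusion for patients "Without surgery or transferred to other departments" gives no timing or reason for a transfer, so it may also act after surgery.

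**The concern.** The Background names wound infection and dehiscence among the complications of interest. A patient operated on for either one after discharge meets the reoperation exclusion as written, so the rule can delete the outcome the study is meant to explain.

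The two clocks also differ. The outcome is timed from surgery and the exclusion from discharge, so the exclusion window always runs past the outcome visit. Potential Risks and Mitigation Strategies says that when poor healing is found at follow-up, "the follow-up personnel will inform patients of appropriate subsequent treatment options". If the treatment chosen is an operation inside the window, a failure already observed at day 30 qualifies for removal.

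Three things are at stake. Events are lost, in a study whose multivariable model needs them. The failure risk is understated. The BRI odds ratio is distorted if removal among failures depends on BRI. The rules on late, refused and lost follow-up add selection whose direction is unknown.

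**Working it through.** The protocol gives no failure risk, reoperation rate, loss rate or length of stay, so there is no figure of its own to reproduce. All inputs below are assumptions, except the 30-day periods and the sample size of 400 (Sample Size Calculation).

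**1. Timing.** With discharge on postoperative day d, the exclusion window closes on day d + 30, and the outcome visit is on day 30. The overhang is d days.

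| Discharge day (assumed) | Window closes | Days after outcome visit |
|---|---|---|
| 3 | 33 | 3 |
| 7 | 37 | 7 |
| 14 | 44 | 14 |

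**2. Events and failure risk.** Assume a 10% risk, that is 40 failures in 400. If a share f of failures is removed, 40(1 − f) events remain among 400 − 40f patients.

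| f | Events left | Observed risk |
|---|---|---|
| 10% | 36 | 36/396 = 9.1% |
| 20% | 32 | 32/392 = 8.2% |
| 30% | 28 | 28/388 = 7.2% |

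**3. BRI odds ratio.** Split the cohort at the median BRI. If the true risk in a half is p and a share f of its failures is removed, the observed risk is p(1 − f)/(1 − pf), so the observed odds are p(1 − f)/(1 − p). If healed patients are removed equally across BRI, then

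observed OR = true OR × (1 − f_upper)/(1 − f_lower),

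whatever the risks. Take 7% (lower) and 13% (upper). True OR = (0.13/0.87)/(0.07/0.93) = 0.1494/0.0753 = 1.99.

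| Share removed, lower / upper half | Factor | Observed OR |
|---|---|---|
| Equal shares | 1.00 | 1.99 |
| 2% / 5% | 0.97 | 1.92 |
| 0% / 5% | 0.95 | 1.89 |
| 5% / 10% | 0.95 | 1.88 |
| 10% / 30% | 0.78 | 1.54 |
| 30% / 10% | 1.29 | 2.55 |

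**4. Missing outcomes.** Suppose a share m of each half has no day-30 outcome because of late review, refusal or loss, and the observed risks are 7% and 13%. The risk in a half then lies between (1 − m)p, with all missing patients healed, and (1 − m)p + m, with all failed. Setting the halves to opposite extremes bounds the OR. For m = 5% the lower half ranges over 0.0665–0.1165 and the upper half over 0.1235–0.1735. The lower bound is odds(0.1235)/odds(0.1165) = 1.07 and the upper bound is odds(0.1735)/odds(0.0665) = 2.95.

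| m | Bounds on an OR of 1.99 |
|---|---|
| 2% | 1.50–2.35 |
| 5% | 1.07–2.95 |
| 10% | 0.68–4.12 |

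These are extreme bounds, not expected values.

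**The case against.** The strongest reply is that the effect on the stated objective is conditional. The Objective section is about association, not incidence, and the odds ratio changes only if removal among failures differs by BRI. Only failures that need an operation after discharge are removed. Those managed without surgery stay in as secondary healing, and reoperation during the index stay is not clearly covered. With modest shares the shift is small (1.88 to 1.92 in the table). Sampling error dwarfs it: with 14 and 26 events in 200 each, the Wald 95% interval is about 1.00 to 3.93. All of that is correct, and it is why no direction or size is claimed. It does not make the rule sound: lost events cost precision even at equal shares, and nothing in the protocol ensures that the shares are equal.

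A second reply is that the rule probably aims at unrelated operations that would disturb wound assessment. That may be the intent, but the text does not say so.

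Third, removal of an already assessed patient is an inference, because no visit after day 30 is described. This is fair. It is something the rule permits, not something the protocol says will happen, although the HIS could show a later operation.

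Fourth, admission data and the HIS may allow excluded patients to be recovered, and sensitivity analyses can be left to the SAP. Recovery is possible if the data are kept, which the protocol does not require. Eligibility itself is set in the protocol, and an SAP cannot restore patients who were never retained.

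**Conclusion.** The concern holds and should be fixed before the study proceeds. As written, the reoperation rule removes wound failures that are operated on after discharge, and its window closes d days after the outcome visit for a patient discharged on day d. These conclusions come from the text alone.

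The numerical effect rests on assumptions. At an assumed 10% risk, removing 10% to 30% of failures leaves 36 to 28 of 40 events per 400 patients and an observed risk of 9.1% to 7.2%. The odds ratio is multiplied by (1 − f_upper)/(1 − f_lower). In the cases shown this ranges from 0.78 to 1.29, and it is 1 when the shares are equal. The direction cannot be derived from the protocol. The follow-up rules add selection of unknown direction. If data on excluded patients are not kept, none of this may be reparable at analysis.

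**What to change.** Amend Participant Selection and the matching sentence in Potential Risks and Mitigation Strategies:

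- Define eligibility only by facts known at surgery. Delete the exclusions for additional surgery, late or refused review and loss to follow-up, and the inclusion criterion that requires complete follow-up.
- Record the date and reason of any second operation. Count wound-related reoperation up to day 30 after surgery as not primarily healed. A patient with an unrelated second operation stays in with the day-30 wound status and the recorded reason.
- State that no event after day 30 removes a patient who has been assessed.
- Prespecify a visit window around day 30 and seek missed outcomes in the HIS.
- Report the number and baseline BRI of patients still without an outcome, with a best/worst-case sensitivity analysis.

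The cost is a protocol amendment and record look-up in a system already in use. The drawback is that some outcomes will come from records instead of the visit, and care given at other hospitals may not appear in this hospital's HIS.

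### The protocol states two different enrolment figures, 400 and 500, and does not say how they relate

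*Protocol*

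**What the plan says.** The Sample Size Calculation section consists of one sentence. It begins "A total of 400 patients undergoing thoracic surgery in the Department of Thoracic Surgery at Tongji Hospital" and ends "affiliated with Tongji Medical College of Huazhong University of Science and Technology, will be enrolled". The Study Procedure section, which follows directly, says "A total of 500 participants are planned for enrollment; subjects not meeting the exclusion criteria will be excluded".

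Three other places bear on how many patients reach the analysis:

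- The Exclusion Criteria include "Failure to review on time or refusal to follow up" and "Additional surgeries within 30 days of discharge from the hospital". Neither can be known until after surgery or discharge.
- Potential Risks and Mitigation Strategies says "Patients lost to follow-up will be excluded from the study".
- Data Collection and Statistical Analysis fixes the time of the outcome: "Wound healing status will be assessed during a follow-up visit 30 days after surgery".

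The protocol gives no expected rate for any of these removals. It contains no amendment history, so both figures are current text.

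**The concern.** Two adjacent sections give different numbers for the same quantity: patients enrolled at the same hospital for the same study. The sentence that might have linked them does not help. Read literally, it removes subjects who do not meet the exclusion criteria, which is the reverse of what the exclusion list intends.

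At stake are the recruitment target and the expected size of the 30-day logistic regression. Suppose the study ends with about 400 patients. That count could be the full enrolment target, the evaluable set expected after removals from 500, or a shortfall of 100 against 500. The protocol cannot tell these apart, so neither completion of recruitment nor attrition can be judged against the plan. This matters because some removals depend on attending follow-up, which is when the outcome is assessed.

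**Working it through.** **Inputs from the protocol.** Enrolment is 400 (Sample Size Calculation) and 500 (Study Procedure). No power, effect size, event rate or removal rate is stated, so neither figure can be reproduced. The check is whether the two can agree.

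**Step 1: the gap.** 500 − 400 = 100 patients. 100/400 = 25% and 100/500 = 20%. This is not a rounding difference.

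**Step 2: can removals link the two figures?** If 400 is the evaluable number and d the fraction removed, enrolment is 400/(1 − d), rounded up. The values of d are assumptions.

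| Assumed removal d | Enrolment needed for 400 evaluable |
|---|---|
| 5% | 422 |
| 10% | 445 |
| 15% | 471 |
| 20% | 500 |
| 25% | 534 |

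The figures agree exactly at d = 20%. The incorrect inflation 400 × (1 + d) also gives 500, at d = 25%. The protocol states neither rate, so even a reader who accepts the link cannot tell which rate was assumed.

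**Step 3: what follows if they are rival enrolment targets.** With the same event rate, covariate spread and removal rate, the standard error of a log-odds coefficient is proportional to 1/√N. The ratio of interval widths, 400 to 500 enrolled, is √(500/400) = 1.118, or about 11.8% wider. A common removal rate cancels:

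| Assumed removal | Evaluable if 500 enrolled | Evaluable if 400 enrolled | Width ratio |
|---|---|---|---|
| 0% | 500 | 400 | 1.118 |
| 10% | 450 | 360 | 1.118 |
| 20% | 400 | 320 | 1.118 |

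**Step 4: effect on event counts.** The secondary-healing rate is not stated. At assumed rates of 5%, 10% and 20%, 400 analysed patients give 20, 40 and 80 events, and 500 give 25, 50 and 100. These counts show only the size of the difference and are not a test of adequacy.

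**Step 5: what follows if they are one cohort.** With 500 enrolled and 400 evaluable, both figures describe the same study. There is then no precision difference, and the defect is only that the numbers are unlabelled.

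**The case against.** The best case for the protocol is that it describes 500 recruited and 400 retained. The inclusion criteria themselves require full clinical data and full follow-up records, so a patient qualifies only once follow-up is complete. On that view, enrolled in the 400 sentence means satisfying all criteria, and the 500 sentence goes straight on to exclusions. This reading is plausible and the arithmetic allows it. It still does not clear the text, because both numbers carry enrolment wording, no sentence connects them, and the reader has to supply the 20%.

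Four narrower objections have some force:

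- Only the statement on loss to follow-up clearly describes a later removal. Treating missed review, refusal and additional surgery as post-enrolment removals is an inference from their timing. It is a reasonable one, but it is not the protocol's wording.
- The 11.8% applies only if the figures are competing enrolment targets.
- A removal assumption could sit in a separate analysis plan. The point therefore rests on the contradiction between two stated figures, not on the missing rate.
- The study is observational, and the protocol states no power calculation, interim look or stopping rule that depends on N. The ambiguity affects recruitment accountability and expected precision. It does not affect the outcome definition or the validity of the tests.

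**Conclusion.** The concern holds. The protocol gives two enrolment figures that differ by 100 patients and offers nothing to reconcile them. It should be fixed, but it does not threaten the validity of the analysis.

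The consequence lies between two cases. Under the enrolled and evaluable reading there is no loss of precision. Under the rival-target reading intervals are about 11.8% wider with 400 than with 500, assuming equal event rate, covariate spread and removal rate. The removal and event rates used in the check are assumptions. The reversed exclusion phrase is a secondary slip, since the list makes the intent plain.

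**What to change.** State one enrolment target and use it in both Sample Size Calculation and Study Procedure.

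- If 500 is the number enrolled and 400 the number expected to have an evaluable 30-day outcome, label them so and state the 20% removal assumed.
- If 400 is the number enrolled, correct the 500 and give the expected evaluable number.

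The sponsor knows which was meant and should choose.

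Two secondary edits would help but are not needed to resolve the contradiction. Reword the Study Procedure sentence so that subjects who meet an exclusion criterion are the ones removed. Describe criteria known only after surgery or discharge as post-enrolment removals, and count them by reason.

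The main fix costs wording in two sections and one stated assumption, with no change to the data collected. Counting removals by reason needs the reason to be recorded. The protocol's variable lists do not include it, so this would be a small addition to the enrolment log if it is not already kept there.
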